 To evaluate the time to onset and resolution of Cryptosporidium infection in participants who developed an infection following an oral administration of ABO809 	 Detection of fecal shedding of C. parvum oocysts by EIA CCI up to 28 days after administration of ABO809 		
	 Time to onset and time to resolution of Cryptosporidium infection following an oral administration of ABO809 		
 To assess the safety and tolerability of ABO809 	 Adverse events, vital signs, ECG findings, safety laboratory assessments including chemistry, hematology, and urinalysis results up to and including the Day 28 visit 		
	 Adverse events of special interest by telephone follow-up after Day 28 through 12 months after ABO809 administration 		

Objective(s) Endpoint(s)

Commercially Confidential Information

3 Study design

This Phase 1 Cryptosporidium CHIM study employs a single-center, open-label design to characterize the incidence of infection and associated symptoms following the administration of single doses of *C. parvum* oocysts (ABO809).

The study will enroll healthy volunteers in cohorts of approximately 10 participants who will receive ABO809 on the same day. A dose level group will receive the same ABO809 dose and can be comprised of multiple cohorts. The first dose level group will start with a cohort of 10 participants who will receive ABO809 at a dose of 1x10⁴ oocysts. The study will continue to enroll participants in the same dose level group if the desired incidences of infection and diarrheal illness are observed, up to a total of approximately 30 participants. If the desired incidences of infection and diarrheal illness are not observed, a new dose level group, receiving ABO809 at a dose of 1x106 oocysts, may be initiated. If needed to optimize the model, intermediate ABO809 doses may be evaluated (see Section 6.5).

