Outpatient follow-up period: After the domicile period, participants will be followed on an outpatient basis ending on Day 56 following the ABO809 administration. Infection is expected to be self-limiting in healthy adults and resolve by Day 21. Published literature on the intensity of infection and oocyst excretion patterns of *C. parvum* in healthy volunteers suggests that oocyst excretion is limited to the first 14 days in up to 86% participants with diarrhea, and excretion prolonged beyond 28 days is observed in only 5% of participants (Chappell et al 1996). Participants will return for follow-up visits on Day 14, 17, 21, 24 and 28 for physical examination and/or to provide collected stool samples (for measurement of oocyst shedding) (see Table 8-1). Safety Follow-Up Calls will be conducted with participants up to Day 56 to collect adverse events that are considered related to administration with ABO809 (see Section 10.1.1.1). Any participants who experience diarrheal symptoms between Day 28 and Day 56 may provide a stool sample for analysis and may return to the study site for an unscheduled visit to consult with the Investigator.

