9.2 Study completion and post-study treatment

Study completion is defined as when the last subject finishes their EOS visit, and any repeat assessments associated with this visit have been documented and followed-up appropriately by the Investigator, or in the event of an early study termination decision, the date of that decision.

Each participant will be required to complete the study in its entirety.

All participants who received ABO809 should have a safety follow-up call conducted approximately 60 days after administration of ABO809. All AEs reported during this time period must be reported as described in Section 10.1.3.

Post-study Follow-Up calls scheduled after the EOS visit will be conducted at 6 and 12 months after the Day 1 visit to collect adverse event of special interest (AESI) information.

Documentation of attempts to contact the participant should be recorded in the source documentation.

10 Safety monitoring and reporting

As part of a CHIM study, AEs associated with Cryptosporidium infection are expected.

AEs and SAEs will be monitored, treated and appropriately recorded by the Investigator from Day 1 until EOS (Day 56). AESI information will be collected at the 6 month and 12 month Post-Study Follow-Up Phone Calls.

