For AEs that are not contained in the "Toxicity Grading Scale for Healthy Adult and Adolescent Volunteers Enrolled in Preventive Vaccine Clinical Trials (2007)", the following categorization will be used:

- Mild: usually transient in nature and generally not interfering with normal activities
- Moderate: sufficiently discomforting to interfere with normal activities
- Severe: prevents normal activities
- 2. The AE relationship (causality) to the study treatment will be assessed for all AEs recorded during treatment and follow-up by the investigator. The criteria for assessing the AE relationship to the study treatment are listed below:
 - a. Related There is reasonable possibility that the study treatment caused the AE. Reasonable possibility means that there is evidence to suggest a causal relationship between the study treatment and the AE.
 - b. Not related There is no reasonable possibility that the administration of the study treatment caused the event.
- 3. The AE duration (start and end dates) or if the event is ongoing, an outcome of not recovered/not resolved must be reported
- 4. Whether the AE constitutes an SAE (see Section 10.1.2 for the SAE definition)
- 5. Its outcome (i.e. recovery status or whether it was fatal)

AEs Follow-up

All adverse events must be treated appropriately. Conditions that were already present at the time of informed consent should be recorded in medical history of the participant.

Once an adverse event is detected, assessment must be made at each visit (or more frequently, if necessary) of any changes in severity, the suspected relationship to the interventions required to treat it, and the outcome. AEs must be followed, in person or by phone call as appropriate, until resolution or until judged to be permanent (i.e. unresolved at the EOS).

Abnormal laboratory values or test results constitute adverse events only if they fulfill at least one of the following criteria:

- they induce clinical signs or symptoms
- they are considered clinically significant
- they require therapy

Clinically significant abnormal laboratory values or test results must be identified through a review of values outside of normal ranges/clinically notable ranges, significant changes from baseline or the previous visit, or values which are considered to be non-typical in participants with the underlying disease.

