10.1.3 SAE reporting

To ensure participant safety, every SAE, regardless of causality, occurring after the participant has provided informed consent and until EOS (Day 56) must be reported to Novartis Safety immediately, without undue delay, under no circumstances later than within 24 hours of learning of its occurrence. Detailed instructions regarding the submission process and requirements are to be found in the Investigator folder provided to the study site. Information about all AEs is collected and recorded on the Serious Adverse Event Report Form: all applicable sections of the form must be completed in order to provide a clinically thorough report.

SAEs occurring after the participant has provided informed consent until the time the participant is deemed a Screen Failure must be reported to Novartis.

All follow-up information for the SAE including information on complications, progression of the initial SAE and recurrent episodes must be reported as follow-up to the original episode

within 24 hours of the Investigator receiving the follow-up information. An SAE occurring at a different time interval or otherwise considered completely unrelated to a previously reported one must be reported separately as a new event.

If the SAE is not previously documented in the Investigator's Brochure and is thought to be related to ABO809, a CMO & PS Department associate may urgently require further information from the Investigator for health authority reporting. Novartis may need to issue an Investigator Notification (IN) to inform all Investigators involved in any study with ABO809 that this SAE has been reported.

Suspected Unexpected Serious Adverse Reactions (SUSARs) will be collected and reported to the competent authorities and relevant ethics committees as per national regulatory requirements in participating countries.

If any SAEs are experienced after EOS (i.e. Post-Study Safety Follow-up calls at 6 and 12 months) in which the Investigator considers there is a reasonable possibility thatABO809 caused the event, the event should be recorded, reported, and captured in the Novartis safety database. All such SAEs will be included in an addendum to the CSR and reported to the competent authorities and relevant ethics committees as per national regulatory requirements in participating countries.

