12.5.2 Safety endpoints

For all safety analyses, the safety set will be used. All listings and tables will be presented by treatment group.

Safety summaries (tables, figures) include data from Day 1 until the EOS with the exception of Baseline data which will also be summarized where appropriate (e.g. change from baseline summaries). In addition, a separate summary for death including on-treatment and post treatment deaths will be provided.

Adverse events

The number (and percentage) of participants with adverse events will be summarized in the following ways:

- by Primary system organ class and preferred term
- by Primary system organ class and preferred term and maximum severity

Separate summaries will be provided for ABO809 related AEs, SAEs, AESIs and deaths.

A participant with multiple AEs within a primary system organ class is only counted once towards the total of the primary system organ class.

Vital signs

All vital signs data will be listed by treatment group, participant, and visit/time and if ranges are available, abnormalities (and relevant orthostatic changes) will be flagged. Summary statistics will be provided by treatment and visit/time.

ECG findings

For ECG parameters, summary statistics for baseline value, actual assessment values, and change from baseline values will be presented by time of measurement. All ECG data will be listed; notably abnormal values will be flagged, and the overall interpretation of abnormality will be presented.

Clinical laboratory evaluations

Clinical laboratory data will include chemistry, hematology and urinalysis results up to EOS.

All laboratory values will be converted into International System of Units (SI) units. If grades are not defined by the Toxicity Grading Scale for Healthy Adult and Adolescent Volunteers Enrolled in Preventive Vaccine Clinical Trials (2007), results will be graded by the low/normal/high classifications based on laboratory normal ranges. Continuous laboratory data will be summarized by presenting summary statistics of raw data and change from baseline values (means, medians, standard deviations, ranges) by time point.

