Outpatient follow-up period: After the domicile period, participants will be followed on an outpatient basis ending on Day 56 following ABO809 administration. Participants will return for follow-up visits on Days 14, 17, 21, 24 and 28 for clinical assessments and to provide collected stool samples for analysis.

Safety Follow-Up Calls: Participants will be contacted by telephone on Days 35, 42, 49 and 56 to collect information on any adverse events that are considered related to administration with ABO809. Any participants who experience diarrheal symptoms between Day 28 and Day 56 may provide a stool sample for analysis and may return to the study site for an unscheduled visit to consult with the Investigator. Additional Post-Study Follow-Up phone calls will be conducted after EOS at 6 and 12 months after ABO809 administration.

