2.6.1 Adverse events (AEs)

AEs and serious adverse events (SAEs) will be monitored, treated and appropriately recorded by the Investigator from Day 1 until EOS (Day 56).

The number (and percentage) of participants with adverse events will be tabulated in the following ways:

- by Primary system organ class and preferred term
- by Primary system organ class and preferred term and maximum severity

A participant with multiple AEs within a primary system organ class is only counted once towards the total of the primary system organ class. If a participant reported more than one adverse event with the same preferred term, the adverse event with the greatest severity will be presented.

Summaries will also be presented for AEs by severity (toxicity grade), for study treatment related AEs, for AEs duration (start and end dates) or if the event is ongoing, of not recovered/not resolved, for whether an AE constitutes an SAE and for its outcome (i.e. recovery status or whether it was fatal).

The most common adverse events reported ($\geq z\%$ in any group for each preferred term in the table by SOC and PT) will be presented in the clinical study report by descending frequency according to its incidence in overall group starting from the most common event. Here threshold value z is set to 5 (%) but it may be updated following review of the dry run outputs.

For the legal requirements of ClinicalTrials.gov, two required tables on treatment emergent adverse events which are not serious adverse events with an incidence greater than 5% and on treatment emergent serious adverse events and SAE suspected to be related to study treatment will also be provided by system organ class and preferred term on the safety set.

If for a same participant, several consecutive AEs (irrespective of study treatment causality, seriousness and severity) occurred with the same SOC and PT:

- a single occurrence will be counted if there is ≤1 day gap between the end date of the preceding AE and the start date of the consecutive AE
- more than one occurrence will be counted if there is >1 day gap between the end date of the preceding AE and the start date of the consecutive AE

For occurrence, the presence of at least one SAE / SAE suspected to be related to study treatment / non SAE must be checked in a block e.g., among AE's in a \leq 1 day gap block, if at least one SAE is occurring, then one occurrence is calculated for that SAE.

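### The Day 35 to 56 safety calls are described as collecting ABO809-related AEs, which contradicts the all-AE rule to Day 56 stated elsewhere; if sites follow the call wording, the pooled AE tables would be biased

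*SAP*

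**What the plan says.** Three scopes for AE collection after Day 28 stand side by side.

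- **Related AEs.** SAP 2.1.1 describes the calls on Days 35, 42, 49 and 56 as made "to collect information on any adverse events that are considered related to administration with ABO809". Protocol 4.1 (outpatient follow-up period) agrees: "Safety Follow-Up Calls will be conducted with participants up to Day 56 to collect adverse events that are considered related to administration with ABO809".
- **All AEs.** Protocol Section 10 states: "AEs and SAEs will be monitored, treated and appropriately recorded by the Investigator from Day 1 until EOS (Day 56"). SAP 2.6.1 repeats this: "AEs and serious adverse events (SAEs) will be monitored, treated and appropriately recorded by the Investigator from Day 1 until EOS (Day 56"). Table 8-1 marks the adverse event row for database entry at Days 35, 42, 49 and 56. Under Protocol 10.1.1, causality "will be assessed for all AEs recorded during treatment and follow-up by the investigator".
- **AEs to Day 28, then AESIs.** The safety endpoint in the Protocol Section 2 objectives table covers AEs, vital signs, ECG and laboratory data, ending with "urinalysis results up to and including the Day 28 visit". The next endpoint is AESIs by telephone from then until 12 months. SAP Table 1-1 repeats both.

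The reporting window is one block. Protocol 12.5.2 states: "Safety summaries (tables, figures) include data from Day 1 until the EOS". SAP 2.6.1 plans AE tables by system organ class and preferred term, a separate summary of related AEs, and a registry table of non-serious AEs with incidence above 5%. None is split at Day 28.

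**The concern.** Table 8-1 schedules no clinic visit between Day 28 and end of study, so the four calls are the only scheduled contacts in that period. The sentence that says what a call is for is the one most likely to become the call script. A related-only script judges causality before the event is recorded, whereas Protocol 10.1.1 asks for non-directive questioning first and a causality assessment of whatever is recorded.

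The study is open label with no control group, so the all-causality AE table is the reader's main check on investigator attribution. If collection narrows after Day 28 while the table still runs to Day 56 with all dosed participants as the denominator, the table mixes two collection rules and does not show it. As written, a site could follow either rule.

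**Working it through.** **Reconciling the text**

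| Source | AE scope, Days 29-56 |
|---|---|
| Protocol 4.1; SAP 2.1.1 | AEs considered related to ABO809 |
| Protocol 10; SAP 2.6.1; Table 8-1 AE row | AEs, no causality filter |
| Protocol 10.1.1 | Causality assessed for every AE recorded in follow-up, which presupposes that unrelated AEs are recorded |
| Protocol Section 2; SAP Table 1-1 | AESIs by telephone |
| Protocol 10.1.3 | SAEs regardless of causality |
| Protocol 10.1.1.1 | AESIs, with a relatedness condition only after EOS |
| Protocol 12.5.2 | Summaries pool Day 1 to EOS |

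The events exposed to the conflict are therefore those that are non-serious, not AESIs, and judged unrelated. The exposed period is Days 29 to 56: 28 of 56 days, or 50%.

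**Direction.** Following the call wording removes only unrelated events and leaves the denominator unchanged. All-causality incidence can only fall, and the related share can only rise.

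**Size.** The plan states no AE rate, so there is no figure to reproduce. What follows is an illustration on assumed inputs:

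- u = mean number of exposed-type unrelated AEs per participant per 28 days, Poisson, assumed 0.1 to 0.6
- r = proportion of participants with one related AE, occurring by Day 28 and independent of the unrelated AEs, assumed 0.6 to 0.9
- after Day 28, either all of these unrelated AEs are collected or none is (the extreme case)

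Formulas:

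- Any-AE incidence: 1 − (1 − r)·exp(−2u) if all are collected; 1 − (1 − r)·exp(−u) if filtered
- Related share of events: r/(r + 2u) if all are collected; r/(r + u) if filtered
- Related share of participants with any AE: r divided by the any-AE incidence

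Results for r = 0.7 (all collected, then filtered):

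| u | Any-AE incidence | Related share of events | Related share of participants |
|---|---|---|---|
| 0.1 | 75.4% → 72.9% | 77.8% → 87.5% | 92.8% → 96.1% |
| 0.2 | 79.9% → 75.4% | 63.6% → 77.8% | 87.6% → 92.8% |
| 0.4 | 86.5% → 79.9% | 46.7% → 63.6% | 80.9% → 87.6% |

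Worked line for u = 0.2: 1 − 0.3·exp(−0.4) = 0.799; 1 − 0.3·exp(−0.2) = 0.754; 0.7/0.799 = 87.6%; 0.7/0.754 = 92.8%.

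Over the grid u = 0.1, 0.2, 0.4, 0.6 and r = 0.6, 0.7, 0.9, any-AE incidence falls by about 1 to 10 points. The related share rises by about 8 to 17 points counted in events and about 1 to 9 points counted in participants.

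**Registry table.** In a dose group of 10, one participant gives 1/10 = 10%, above the 5% threshold. In a group of 30, 1/30 = 3.3% is below it and 2/30 = 6.7% is above. One or two uncollected events can decide whether a preferred term appears.

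**The case against.** The strongest reply is that the operative rules already require all AEs. Protocol Section 10 and SAP 2.6.1 set no causality filter, and Table 8-1 requires database entry at each call. The two related-AE sentences sit in a rationale section and a definitions section, and neither contains the word only. Protocol 9.2 also asks that all AEs be reported for the call at about 60 days. If sites work from these rules, there is no bias. This stands, and it is why the point is a contradiction to be resolved.

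Three stronger readings are tempting, and the documents do not support them.

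- **That late joint or eye pain would be lost.** Protocol 10.1.1.1 makes new-onset non-intestinal symptoms, including these two, AESIs, and applies relatedness only after EOS. SAEs are covered explicitly: Protocol 10.1.3 requires reporting of "every SAE, regardless of causality, occurring after the participant has provided informed consent and until EOS (Day 56").
- **That no all-causality information is collected in Days 29 to 56.** SAEs and AESIs still are. The schedule also asks for concomitant medications at the calls, and AEs volunteered by participants can be recorded.
- **That AE totals are understated by a fixed fraction, such as a third.** That needs related AEs to continue at the same rate after Day 28. Protocol 4.1 expects infection to resolve by Day 21, so related AEs should cluster early, and no AE rate is given.

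It is also fair that the main AE tables count participants, that a related share is not itself a planned output, and that without a control arm no between-arm comparison is affected. The first two points reduce the practical effect. The share can still be read by setting the related-AE summary beside the all-AE table.

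**Conclusion.** The point holds as an internal contradiction that should be corrected. Two sentences, one in each document, describe the Day 35 to 56 calls in a way that conflicts with the AE collection rule stated elsewhere and differs from the objectives table. A reader might infer that the plan has adopted related-only collection and that the AE results are distorted. The documents support only the conditional statement: if sites follow the call wording, non-serious, non-AESI AEs judged unrelated would be under-collected in Days 29 to 56. The pooled all-causality incidence, including the registry table of non-serious AEs above 5%, would then be biased downward, and related AEs would look like a larger share.

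The direction follows from the text. The size does not: the ranges shown rest on assumed rates and on complete loss of the exposed events after Day 28. The AE endpoint to Day 28 is unaffected.

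**What to change.** Reword the call descriptions in Protocol 4.1 and SAP 2.1.1 so that the Day 35, 42, 49 and 56 calls collect all AEs regardless of causality, with relatedness assessed after recording. This matches Protocol 10, Protocol 10.1.1, SAP 2.6.1 and Table 8-1. Then reconcile the objectives tables (Protocol Section 2, SAP Table 1-1) so that one AE scope is stated for Days 29 to 56.

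If the sponsor does intend related-only calls, amend the all-AE statements instead, end the all-causality AE tables at Day 28, and report later related AEs, AESIs and SAEs in a separate table.

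The cost is two reworded sentences, a matching edit to the objectives tables and a few more unrelated AEs to record; the calls and the AE form already exist. Splitting the tables into Days 1-28 and 29-56 is optional once the wording is aligned.

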2.1.1.1 Definition of clinical and parasitological response

Diarrhea: A participant will be considered as having diarrhea if they have at least one stool sample grading 3-5 on the Stool Grading System (Table 5-5). Grade 1-2 stools are considered normal and are formed or soft stool which do not easily take the shape of the container. Grade 3-5 stools are considered diarrheal and are thick liquid, opaque watery, rice water or clear watery stool which do take the shape of the container.

Number of days to diarrhea onset: is defined as the first diarrhea stool date minus the dosing date.

Number of days of diarrhea: is defined as all days with at least one stool sample grading 3-5.

Number of days to resolution of diarrhea: is defined as the last diarrhea stool date minus the dosing date +3

Duration of diarrhea (hours): is defined as the last diarrhea stool date/time minus the first diarrhea stool date/time.

Clinical diarrheal illness: A participant will be considered as having clinical diarrheal illness if diarrhea is observed with at least two diarrheal bowel events within 24 hours on at least two days during the observation period beginning after ABO809 administration (Day 1) and ending on Day 28.

Resolution of clinical diarrhea illness: A participant will be considered recovered from diarrheal illness when no diarrhea occurred on ≥ 2 consecutive days following the last diarrhea in participants with clinical diarrhea illness.

Number of days to clinical diarrhea onset: is defined as the first day of clinical diarrhea illness date minus the dosing date.

Number of days of clinical diarrhea illness: is defined as all days of diarrhea in participants with clinical diarrhea illness. It will be set to 0 for participants with no clinical diarrhea illness.

Confidential

Number of days to resolution of clinical diarrhea illness: is defined as 48 hours after the last day of clinical diarrhea illness, i.e., last diarrhea date minus the dosing date +3 in participants with clinical diarrhea illness.

Duration of clinical diarrheal illness (hours): is defined as the last diarrhea date/time minus the first diarrhea date/time in participants with clinical diarrhea illness.

Cryptosporidium infection: is defined as the presence of oocysts in at least 1 stool sample starting 72 hours following the administration of ABO809 (or sooner if associated with symptoms suggestive of diarrheal illness), up to Day 10 or Day 28 (separately). If clinical symptoms associated with cryptosporidiosis occur earlier than 72 hours post-administration, then stool samples after the onset of symptoms can be collected for parasitological evaluation. Oocysts will be detected by a commercially available diagnostic EIA test and confirmed by a DFA test if the EIA is positive. The tests will be performed at a Clinical Laboratory Improvement Amendments (CLIA) certified laboratory. Samples that test negative for Cryptosporidium by EIA will be reported as negative for Cryptosporidium without confirmation by DFA.

Resolution of *Cryptosporidium* **infection:** A *Cryptosporidium* infection will be considered resolved when no evidence of *Cryptosporidium* is detected in stool samples collected over ≥ 2 consecutive days. Please refer to the definition of "Number of days to resolution of Cryptosporidium infection" for further details.

Number of days to Cryptosporidium infection onset: is defined as the first occurrence of positive EIA test if it is at/after 72 hours post-challenge, otherwise as the first occurrence of positive EIA test with clinical diarrhea symptoms (if earlier than 72 hours), minus the date of dosing.

Number of days of Cryptosporidium infection: is defined as all days that have at least 1 positive EIA test.

Number of days to resolution of Cryptosporidium infection: is defined as:

- 48 hours after the last occurrence of positive EIA test during the inpatient period following the initial admission into the unit or,
- 48 hours after the last occurrence of positive EIA test during the inpatient period following the readmission into the unit or during the outpatient period up to Day 20 (without clinical diarrhea symptoms and before the start of NTZ) or,
- if there is a clinical relapse during the outpatient period, 48 hours after the last occurrence of positive EIA test with GP60 result showing recrudescence or,
- if clinical relapse during the outpatient period with GP60 result showing reinfection, 48 hours after the last occurrence of positive EIA test before onset of clinical symptoms,

i.e., the last positive EIA test date minus the dosing date +3.

Duration of *Cryptosporidium* **infection:** is defined as the last *Cryptosporidium* infection date/time minus the first *Cryptosporidium* infection date/time.

Recrudescence: A *Cryptosporidium* infection will be considered as recrudescent if *Cryptosporidium* infection occurs again after resolution of infection with a genotype identical

to that of *Cryptosporidium parvum* Iowa isolate used for this study. Recrudescence must be confirmed by Gene Encoding Glycoprotein 60 kDa Protein (GP60) genotyping analysis.

Reinfection: A participant will be considered as reinfected if *Cryptosporidium* infection occurs again after resolution of infection with a genotype different from the *Cryptosporidium parvum* Iowa isolate used for this study. Reinfection must be confirmed by GP60 genotyping analysis.

Secondary transmission: Person-to-person transmission of *Cryptosporidium* may occur, particularly among study participant's household members or sexual partners.

